The antiretrovirals used in the treatment of HIV infection have been previously studied *in vitro* and *in vivo* for SARS (Severe Acute Respiratory Syndrome) and MERS (Middle East Respiratory Syndrome) (50,51). Particularly, in this pandemic some observational studies have identified a smaller number of patients with HIV acquiring COVID-19 in comparison to the general population which has brought attention to the scientific community (52).

In silico studies have identified antiretroviral drugs with potential capability of binding the catalytic center of RdRp such as Nucleoside Reverse Transcriptase Inhibitors: abacavir, emtricitabine, lamivudine, zidovudine and tenofovir, also protease inhibitors such as: lopinavir, ritonavir, saquinavir and the booster cobicistat (53-55). This information has been confirmed *in vitro* studies for TDF, which acts as analogue of a nucleotide that early finishes the replication of the RNA strand (55).

Cytotoxic and antiviral effects of some of the molecules have been evaluated in fibroblasts from human lung cells. For tenofovir and emtricitabine (TDF/FTC) the EC50 and the TC50 higher than 100 μ M, however, it is inferior compared to remdesivir which might be explain for the type of assembling to the RdRp in each case (48).

Furthermore, Park, *et al.* developed an animal model of SARS-CoV-2 in ferrets in which the pathogenicity, transmissibility, and lung damage caused by the virus were demonstrated. In an experiment using this model, the virus was inoculated by the intranasal route, and a day after, numerous molecules with potential antiviral effect were administrated. These molecules were: Lopinavir/Ritonavir, Hydroxychloroquine, TDF/FTC. The duration of the intervention was 14 days and the ferret group given TDF/FTC presented lower temperature compared to the control group, and also an earlier recovery from signs including cough, rhinorrhea, and reduction of activity. Moreover, a lower load of virus was detected in the nasal samples from ferrets in the intervention group. From the drugs studied TDF/FTC showed the best results in reducing clinical signs and clearing nasal viral shedding (46).

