3.1. Study design

Randomized triple-blinded multicentric clinical trial, conducted in parallel, with two arms:

The trial will be performed with health care workers (Physicians, Nurses, Respiratory therapists, or nurse assistants) free of SARS-CoV-2 infection prior, recent or at the time of the inclusion and who directly care for confirmed or suspected cases of COVID-19 in the emergency room, general COVID wards or intensive care units. A screening at baseline will be carried out in order to evaluate for eligibility by performing: SARS-CoV-2 RT-PCR, SARS-CoV-2 IgG antibodies, as well as, hemogram, creatinine, serum phosphorus, AST, ALT, ELISA for HIV, surface Hepatitis B antigen antibodies, qualitative pregnancy test (b-HCG). Once

eligibility is verified participants will be randomly assigned to either an intervention or a control group.

The interventions consists in the administration of Tenofovir/ Emtricitabine (300 mg / 200 mg daily during 60 days) + Personal Protective Equipment (PPE) and the control consists in the administration of placebo (1 tablet daily during 60 days) + Personal Protective Equipment (PPE)

All participants will have PPE recommended for the preventions of COVID-19 by the WHO which include mayo dress, nonfluid long sleeve gown, ocular protection with goggles, face shield or visor and surgical mask in procedures that do not aerosolize. N-95 respirators are required for procedure that generate aerosols. For detailed description see Table 2.

The re-use of N-95 respirators will be allowed according to CDC and WHO guidelines. This taking into consideration the shortage of supplies for the actual situation. The N-95 continuous use will be for 8 hours and the N-95 intermittent use will be allowed up to 5 times with the precaution of storage in a paper and plastic bag label them with the participant name and placed them in a plastic recipient at the end of shifts(48).

After baseline evaluation and confirming eligibility an initial visit and 4 follow up visits at day 20, 40, 60, 75 days will be carried out. See Table 1 and Graph 1.

In the case of presenting COVID-19 related symptoms at any time after enrolling a SARS-CoV2 RT-PCR will be performed between day 1 to 5 of the onset of symptoms and will be repeated it after 72 hours in case that the first one is negative. In the case of having any positive SARS-CoV2 RT-PCR or SARS-CoV2 IgG SARS-CoV2 infection will be confirmed and the intervention will be suspended.

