3.4. Sample size

An estimative of the number of required participants was done according to the following parameters:

- Risk of SARS-CoV-2 infection reported in the world: despite of the little data available on incidence reports from China, The Netherlands and Madrid vary from 6 to 38.9 per 100 exposed health care workers. The high variability on the incidence is related to the develop of institutional outbreaks, thus establishing a latent risk in all hospital institutions in a pandemic scenario (7,44,76). To assess the sampling size calculation for this study, besides what has been reported internationally, an approximate calculation of the incidence of SARS-CoV-2 infection in the health care institutions in which the study will be held was performed. It is important to know the infection and epidemic control variates from one institution to another. While some actively screen asymptomatic health care personnel others only screen symptomatic health care personnel. The incidence observed in a 2-month period of time variates between 3.3% and 13.7% with a mean of 11.2 cases per 100 health care workers.

Based on that preliminary information, an expected risk for SARS-CoV-2 infection in the control group (Placebo + PPE) of 0.10 was used for the calculation. With the objective of estimating precisely a 50% relative risk reduction an assumption of an expected risk of 0.05 was done in the intervention group (Tenofovir/Emtricitabine + PPE) in order for a difference of 0.05 to detect between both groups.

- Power: 0,80. Alfa level: 0.05
- Assigantion ratio $n_1/n_2 = 1:1$ (randomization1: 1).
- Sample size: 858 (429 per group).

Considering possible loses up to 10% it is risen to 950 in total (with randomization 475 participants to each group).

As a limitation of the study, if the incidence or the effect of the interventions are considerably lower than expected, the power to detect significant differences between both groups will be reduce. However, due to the progression of the pandemic in our country, with a tendency to increase, it is probable that the incidence observed in health care professionals will remain stable or even increase not only for the intrahospital risk, but for the risk in the community,

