3.6. Procedures

In table 1. Detailed follow up evaluations are described.

Table 1. Description of the evaluations to be done during the trial.

Follow up table				
Day	General activity	Specific activity	Responsible	Result
0	Base line diagnoses	Initial Clinical evaluation	Medical doctor of the study	Evaluating inclusion and exclusion criteria. Signing informed consent form
		Blood samples	Nurse Lab tech	Laboratory report: hemogram, creatinine, phosphorus, AST, ALT HIV ELISA, HB Surface antigen antibodies
		SARS-CoV-2 RT-PCR sampling	Respiratory therapist or nurse	Result of SARS-CoV-2 RT-PCR
		SARS-CoV-2 IgM and IgG antibodies	Nurse Lab tech	Result of IgM and IgG antibodies
		b-HCG sampling in women	Nurse Lab tech	Report of b-HCG
20	Visit 1	Clinical evaluation	Medical doctor of the study	Clinical record and eCRF for clinical evaluation, adherence, and adverse events

40	Visit 2	Blood sample for: SARS-CoV2 IgM, IgG antibodies and blood chemistry	Nurse Lab tech	Laboratory report of SARS-CoV2 IgM, IgG antibodies and creatinine
		Clinical evaluation	Medical doctor of the study	Clinical record and eCRF for clinical evaluation, adherence, and adverse events
60	Visit 3	Blood samples	Nurse Lab tech	hemogram, creatinine, phosphorus, AST, ALT HIV ELISA, HB Surface antigen antibodies b- HCG in women
		SARS-CoV-2 RT-PCR sampling	Respiratory therapist	Result of SARS-CoV-2 RT-PCR
		Clinical evaluation	Medical doctor of the study	Clinical record and eCRF for clinical evaluation, adherence, and adverse events
75	Visit 4	Blood samples	Nurse Lab tech	Laboratory report of SARS-CoV2 IgG
		Clinical evaluation	Medical doctor of the study	Clinical record and eCRF for clinical evaluation,
		End of follow up and communication to study subject	Clinical coordinator	Minutes

During follow up to any participant who develop COVID-19 related symptoms at any time after randomization given by two or more of the following: Body temperature higher than 38 Celsius, cough of recent onset (in the previous 10 days), dyspnea,odynophagia, malaise, fatigue, acute diarrheal disease, ageusia, dysgeusia, anosmia or hyposmia, an RT-PCR will be performed within the next 5 days and will be repeat it if the result is negative and the symptoms persist. This RT-PCR will be performed at every of the centers of the study and will request the patient the immediate report of the symptoms through an app or via phone call. In case of a positive RT-PCR the infection

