will be confirmed. While confirmation RT-PCR arrives, the participant will not quit taking the intervention. In that scenario, the intervention will only be suspended in the case of a highly suspected case or severe case requiring hospitalization.

In case the infection is ruled out in the follow up, the participant will continue the interventions and follow up scheduled, according to graph 1.

With regards to diagnostic testing during follow up as shown in table 1. IgG antibodies will be done at visit 2 and 4 (40 days from initially taking the intervention and 15 day after finalizing it). This considering volunteer that might acquire the infection in the last days of the pharmacological intervention. Moreover, at day 60, last of the intervention, an RT-PCR will be performed to all participants. This in order to detect participants who develop asymptomatic infection. The research group is aware that this follow up will not identify a 100% of the asymptomatic infection for the low sensitivity of testing in this scenario, approximately 30 to 40% (46,47), yet it will be done in both arms.

Importantly, for the covid-19 emergency, clinical follow up, adverse event reporting and adherence reporting could be done online.

Personal Protective Equipment

All volunteers will be using the following personal protective equipment. This based on the guidelines of the WHO (23). See table 2.

Table 2. Use of PPE by study volunteers.

Area	Health care personnel or patients	Activity	Type of PPE or activity
Emergency room, general COVID wards or intensive care units	Health care workers	Direct contact with the patient of non-aerosol generating procedures.	Surgical mask Visor or glasses. Long sleeve gown Nonsterile gloves.
		Direct contact with the patient and aerosol generating procedures.	N95 respirator Visor or glasses. Long sleeve gown Nonsterile gloves. May dress

			under the robe that is removed at the end of the shift
Other areas of transit (hallways or waiting rooms)	All personnel including health care workers	Any activity that does not involve contact shorter than 2 meters in distance between people	Surgical mask

Adapted from: Rational use of personal protective equipment for coronavirus disease 2019 (COVID-19). Interim guidance 27 February 2020. World Health Organization. (23)

*Health care worker: person in whose activity directly care a contact, suspected, or confirmed case of COVID-19.

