5.2 Benefit for volunteers

The study is based on previously reported findings in the scientific literature regarding the potential ability of tenofovir disoproxil/emtricitabine to inhibit SARS-CoV-2 replication (13, 47–50). Therefore, volunteers could benefit from the reduced risk of developing COVID-19 which could mean a decreased risk of developing symptoms, temporary disability, hospitalization, transmission to family members and close contacts, and to other members of the community. Among the possible complications associated with COVID-19, it could reduce the severity or risk of mortality during the follow-up period. Additionally, the continuous and accessible use of EPP for the study volunteers reduces the risk of contagion by COVID-19. The findings of the present study could lead to a change in public policies that in the future will reduce the risk of acquiring COVID-19 by health personnel. In accordance with current Colombian regulations, volunteers will not receive any type of financial compensation for their participation in the study.

6. Report of adverse events

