9.1 Technical services

No.	Item	Site	Justification	Quantity	Unit value (cop)	Subtotal (cop)
1	Civil liability policy for volunteers and clinical trial personnel	Pontificia Universidad Javeriana	Regulatory agency requires a liability protection for both, volunteers and clinical trial personnel regarding risks during COVID-19 pandemic.	1	\$ 96,101,872.44	\$ 96,101,872.44
2	Clinical laboratory tests (Creatinine; CBC; ALT; AST; BHCG in women, antiHBS; HIV, IgG Antibodies; Serum phosphorus, CRP)	Pontificia Universidad Javeriana	Laboratory exams required at baseline and follow-up	1	\$ 535,959,372.00	\$ 535,959,372.00
3	rtPCR for symptomatic volunteers (7,5%)	Pontificia Universidad Javeriana	rtPCR for follow-up 1, for volunteers who develop respiratory symptoms (estimated of 7.5%)	71	\$ 250,000.00	\$ 17,750,000.00
4	Laboratories for follow-up 2 (creatinine and antibodies)	Pontificia Universidad Javeriana	Laboratory tests for 950 volunteers	1	\$ 50,071,650.00	\$ 50,071,650.00
5	RtPCR including transport media for follow-up 2.	Pontificia Universidad Javeriana	Laboratory tests. It is estimated that 7.5% of volunteers will develop symptoms that require rtPCR. Services will be provided by recruitment sites	71	\$ 250,000.00	\$ 17,750,000.00
6	Laboratory tests (Creatinine, CBC, ALT, AST, BHCG for women (80% of volunteers) and rtPCR for all subjects.	Pontificia Universidad Javeriana	Laboratory tests for each participant (80% women; 20% men)	1	\$ 285,512,810.00	\$ 285,512,810.00
7	IgG antibody tests for follow up 4	Pontificia Universidad Javeriana	IgG antibody tests for follow up 4	1	\$ 43,320,000.00	\$ 43,320,000.00
8	Recruitment services	Pontificia Universidad Javeriana	Recruitment costs per volunteer including PPE + workhours of pharmaceutical chemist, respiratory therapist, assistant nurse, and laboratory assistant	950	\$ 105,699	\$ 100,414,240
						\$1,146,879,944

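### Equal test schedules in both arms do not rule out bias toward benefit if the drug reduces symptoms, because part of the testing is triggered by symptoms

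*Combined protocol and SAP*

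**What the plan says.** Testing for the primary outcome has two layers.

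- **Scheduled, for every participant:** IgG at Visit 2 (day 40) and Visit 4 (day 75), and RT-PCR at day 60, the last of these expressly to find asymptomatic infection (section 3.6 and Table 1).
- **Triggered by symptoms:** two or more listed symptoms lead to an RT-PCR, a possible repeat, and IgM/IgG 14 days after onset when RT-PCR stays negative (sections 3.1 and 3.6).

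On the repeat RT-PCR the two sections differ. Section 3.1 says it "will be repeated it after 72 hours in case that the first one is negative". Section 3.6 says it "will be repeat it if the result is negative and the symptoms persist".

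Section 3.3 counts any positive RT-PCR or any positive IgG, with or without symptoms. Section 3.6 concedes that not all asymptomatic infections will be found and puts sensitivity at "approximately 30 to 40% (46,47), yet it will be done in both arms". It adds nothing on detection that differs by symptom status. Section 4 plans a Kaplan–Meier estimate and a Cox model for infection, and describes severity only among participants found infected.

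**The concern.** The same schedule in both arms protects the comparison only if an infection is equally likely to be found in each arm. Here a symptomatic infection gets extra tests and an asymptomatic one does not. If the drug turned symptomatic infections into asymptomatic ones, fewer would be found on the drug even though just as many occurred. The error would always favour the drug.

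The possibility is not far-fetched on the protocol's own background. Section 1.3 reports that treated ferrets had "earlier recovery from signs including cough, rhinorrhea, and reduction of activity". The main objective is prevention of infection, so a result produced partly by milder illness would answer a different question. As planned, the analysis could not show which had occurred.

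**Working it through.** **1. The plan's own figure.** Section 3.4 gives the inputs: "an expected risk for SARS-CoV-2 infection in the control group (Placebo + PPE) of 0.10 was used for the calculation", and "an assumption of an expected risk of 0.05 was done in the intervention group". With power 0.80 and two-sided alpha 0.05 (sidedness is not stated):

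n = [1.96·√(2·0.075·0.925) + 0.842·√(0.10·0.90 + 0.05·0.95)]² / 0.05² = 435 per group.

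The plan states 429; an arcsine formula gives 424. Allowing for 10% losses, 858/0.9 = 954, against 950 stated. The sample size reproduces and is not in dispute.

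**2. Model for the bias.** Assume the drug has no effect on infection. Let a be the asymptomatic share of infections, and Ss and Sa the probabilities that a symptomatic or an asymptomatic infection is found at any time in follow-up.

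- Found = (1 − a)·Ss + a·Sa
- Apparent ratio = Found on drug / Found on placebo
- P(false significant benefit) = Φ{[d√n − 1.96√(2p̄(1 − p̄))] / √(p₁(1 − p₁) + p₂(1 − p₂))}, with n = 475, p₁ = 0.10, p₂ = 0.10 × ratio, d = p₁ − p₂

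Ss = 0.90–0.95 is an assumption. The shift in a is also an assumption. The values 18% and 46.5% are the ends of the range that section 1.3 quotes from screening studies in confined populations. They are not a drug effect. The shift from 30% to 60% is purely illustrative.

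**3. How many asymptomatic infections would the scheduled tests find?** Assume infections uniform over 75 days, IgG detectable from day 15 after infection, RT-PCR positive on days 3–17, and independent test results. With g the IgG and p the RT-PCR sensitivity:

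- infected by day 25 (25/75 = 0.333): two IgG chances, 1 − (1 − g)²
- infected days 43–57 (14/75 = 0.187): one IgG and the RT-PCR, 1 − (1 − g)(1 − p)
- infected days 25–43 and 57–60 (21/75 = 0.28): one IgG, g
- infected after day 60 (0.20): none

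If 30–40% is a per-test figure for both tests:

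- g = p = 0.3: 0.333·0.51 + 0.187·0.51 + 0.28·0.3 = 0.35
- g = p = 0.4: 0.333·0.64 + 0.187·0.64 + 0.28·0.4 = 0.44

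If it describes RT-PCR only (p = 0.4) and IgG performs better:

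- g = 0.7: 0.333·0.91 + 0.187·0.82 + 0.28·0.7 = 0.65
- g = 0.9: 0.333·0.99 + 0.187·0.94 + 0.28·0.9 = 0.76

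If 30–40% already describes the whole programme, Sa is 0.30–0.40. So the low case is Sa = 0.30–0.44 and the high case 0.65–0.76.

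**4. Results: apparent ratio (chance of a false significant benefit, nominal 2.5%).**

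| Sa | 18%→46.5%, Ss 0.90 | 30%→60%, Ss 0.90 | 18%→46.5%, Ss 0.95 | 30%→60%, Ss 0.95 |
|---|---|---|---|---|
| 0.30 | 0.78 (21.4%) | 0.75 (27.5%) | 0.78 (22.5%) | 0.74 (29.2%) |
| 0.44 | 0.84 (13.5%) | 0.82 (16.1%) | 0.83 (14.6%) | 0.81 (17.6%) |
| 0.65 | 0.92 (6.4%) | 0.91 (6.9%) | 0.90 (7.2%) | 0.90 (7.9%) |
| 0.76 | 0.95 (4.2%) | 0.95 (4.4%) | 0.94 (4.9%) | 0.94 (5.2%) |

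Worked cell: 0.82·0.90 + 0.18·0.30 = 0.792; 0.535·0.90 + 0.465·0.30 = 0.621; 0.621/0.792 = 0.78.

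If a person whose IgG is missed at day 40 is also missed at day 75, the first term in step 3 becomes 0.333·g. The high case then falls to 0.58–0.73 and, at Ss = 0.90, the ratio to about 0.88–0.94 (5–9%). If Sa = Ss, the ratio is 1.00 and there is no bias.

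**5. Would Visit 4 IgG alone do better?** Assume IgG sensitivity 0.95 in symptomatic infection. The timing factor cancels, so the ratio is [(1 − a)·0.95 + a·g] on drug over the same on placebo. For g = 0.3–0.4 it is 0.74–0.82, no better than the primary analysis. For g = 0.7–0.9 it is 0.91–0.98.

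**The case against.** The strongest reply is that everyone is tested whatever their symptoms, three times after baseline, and that a positive IgG alone meets the endpoint. That stands, and it is why the bias is partial and may be small. It relies on section 3.3 governing the endpoint. The outcome variable in Appendix 3 names RT-PCR only, which would leave the day-60 swab as the sole scheduled safeguard.

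Several stronger readings are tempting and are not supported.

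- A reader might infer that RT-PCR is done only on symptoms, or that the plan calls missed cases harmless. Section 3.6 includes the day-60 RT-PCR for all and openly states a limitation; it just does not address differential detection.
- A reader might take the 13–29% false-benefit range as the expected size. It needs detection of only 30–44% across all scheduled tests, and the text does not say whether 30–40% refers to RT-PCR, to each test or to the whole programme.
- Section 5.2 mentions a "decreased risk of developing symptoms", but as a consequence of less COVID-19; only its next sentence raises severity. The ferrets were treated after inoculation and also had lower nasal viral load, so they are not evidence of symptom relief with infection unchanged.
- The end of follow-up at the first positive (section 4) defines time at risk. It does not say that Visit 4 sampling is cancelled. The line "IgG antibody tests for follow up 4" in section 9.1 divides exactly by 950 (43,320,000/950 = 45,600), which suggests a budget for everyone, although the kit counts in section 9.2 do not match that.
- Visit 4 seropositivity might look like a cure, or a condition for claiming prevention. Step 5 shows that where the bias is large it would repeat the biased answer.

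**Conclusion.** The concern holds in limited form. Equal schedules do not give equal detection if the drug changes the symptomatic share, the error runs toward benefit, and section 4 contains nothing to reveal it.

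Under the assumed shifts and no true effect, the apparent ratio is about 0.74–0.84 if scheduled tests together find 30–44% of asymptomatic infections. It is about 0.91–0.95, with a 4–7% false-benefit chance, if asymptomatic IgG sensitivity is 70–90% and symptomatic detection is 90%. Less favourable choices for the second case (95% symptomatic detection, or repeated IgG misses in the same person) move it to about 0.88–0.90 and 8–9% at the lower end.

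Section 1.3 says that serology accuracy in asymptomatic people is not known with certainty, so the documents cannot settle which case applies. Symptomatic detection, infection timing and the shift itself are assumptions. Nothing in the documents shows that the drug reduces symptoms without preventing infection; the point is that the planned analysis could not tell if it did. The analysis plan should be amended; the trial need not be redesigned.

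**What to change.** 1. Pre-specify, with all randomised participants as the denominator, the comparison by arm of symptomatic and of asymptomatic infections, and of infections first found by a triggered and by a scheduled test. Fewer symptomatic but more asymptomatic infections on the drug would point to symptom reduction rather than prevention.
2. Pre-specify a supportive sensitivity analysis that uses only symptom-independent tests, with the Visit 4 IgG taken in every randomised participant, including those already positive. It should not be a condition for the primary conclusion. State its limits: it removes only the part of the bias due to testing intensity, it has fewer events, and it does not correct a weaker antibody response in asymptomatic infection.
3. Reconcile sections 3.1 and 3.6 on when a negative RT-PCR is repeated.

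Cost: on the design assumptions, 475 × 0.10 + 475 × 0.05 ≈ 71 participants would already be positive and need one draw at an existing visit. The rest is wording in section 4 and in the procedures.
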